# **Material and Methods:**

#### 1) DESIGN

The study presents a randomized design (rTMS vs simulated stimulation) in patients with a single stroke of less than 6 months of evolution and unialteral involvement, who have a brachial paresis with scores on the Fugl Meyer scale (FM)  $\geq$  22 in the upper limb. The different clinical evaluations (previous and result of the intervention) will be carried out blindly with respect to real or simulated rTMS realization. To do this, patients will be selected who come to our center on an admission or outpatient basis.

The intervention phase will last 3 weeks (daily sessions from Monday to Friday), completing a final of 15 sessions. In each session EMTr would be performed first and immediately the rehabilitation treatment of the upper limb based on the protocol of our center (1 specific hour, within the integral program). Evaluations will be made before the intervention, at the end of the intervention and one month later.

• Patients: Patients with a stroke (ischemic-hemorrhagic) that conditions a unilateral limitation (brachial monoparesis or hemiparesis) and that presents a moderate or mild deficit (motor score on the FM scale  $\geq$  22 at motor level of the upper extremity) .To Participate in the study the patients must sign an informed consent and be > 18 y.o. Patients with epilepsy or those with electrical devices in their body or metallic ones in the brain, as well as patients with craniotomy without cranioplasty, will be excluded from the study. All patients whose medical conditions prevent them from complying with the rehabilitation protocol will be excluded

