- rTMS: Patients will be distributed randomly in real or sham rTMS before the specific rehabilitation treatment. To do this, a Magstim Super Rapid magnetic stimulator (Magstim Company, Whitland, Wales, UK) equipped with a double cone coil was used to position it on the cranial cortex. Simulated stimulation will be performed by placing the same coil without being connected, but maintaining the characteristic noise of the stimulation (all this assembly will be kept out of the patient's visual field). The rTMS intensity is calculated over 90% of the motor threshold, evaluated by EMG of surfaces, of the first dorsal interosseous of the hand without motor involvement. From this intensity, adjustments can be made depending on the tolerance. This system has been previously carried out in different studies of ours and other groups for different pathologies, proving safe and tolerable. For rTMS 1500 pulses of 1 Hz frequency will be used at the sub-threshold intensity commented on the optimal score in M1 of the unaffected hemisphere (in relation to the first interosseous dorsal muscle). The simulated rTMS will be applied during the same time. The patient will be in a sitting position while the technique is performed.
- Rehabilitation treatment of the upper limb: The rehabilitation treatment protocolized in our center will be followed within the comprehensive stroke treatment program. According to this protocol, there would be differences between a moderate patient (FM upper extremity motor between 22 and 45) and mild (FM upper limb motor greater than 45).
- Moderate: Active mobility work, proprioceptive treatment, exercises with reality virtual and biofeedback and use of robotic systems with multiple repetitions.
- Mild: Work of active mobility, proprioceptive treatment, exercises with reality virtual and biofeedback, as well as restrictive therapy.

In any case, to compensate for the potential variability of rehabilitative work, the therapist will be blind to the condition of real or simulated stimulation of the patient.

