- Clinical evaluation: A specific clinical evaluation will be carried out before, at the end of the treatment and a month after the same. In this evaluation the FM, Block Test, 9- HPT and ARA Test scale will be evaluated. In turn, spasticity in the muscle groups of the upper extremity will be evaluated using the modified Ashworth scale (Bohanson & Simth 1987) and an analogue numerical scale (from 1 to 10) according to the patient's assessment. In turn, demographic data (sex, age) and stroke characteristics (classification, location, NIHSS) will be registered in the first visit.
- Neurophysiological evaluation: The neurophysiological evaluation will be carried out before the first session and after the end of the intervention phase. The evaluation will be performed with the patient seated, using Ag-AgCl bipolar surface electrodes and a routine electrodiagnostic device using bipolar Ag-AgCl surface electrodes and a CED Spike electrodiagnostic device (CED Micro 1401 analog-to digital system). The motor evoked potentials of the first dorsal interosseous of hand hands will be evaluated, calculating the motor threshold, the recruitment curve and the paired impulse curve. For this, stimuli will be performed by Magstim Super Rapid EMT (Magstim Company, Whitland, Wales, UK) equipped with a focal coil to position it on the cranial cortex. The minimum threshold will be considered to be the motor threshold for at least 5 evoked potentials of at least 50 μV in 10 stimuli.
- Statistical analysis: Changes in the clinical scales (FM and ARA Test) between the two groups will be compared by means of nonparametric tests (Mann-Whitney T test) or, if the normality (Kolmogorov-Smirnov) is not rejected, the TTest test. In addition, the response variables (in these three tests) will be related to various demographic, neurophysiological variables and the characteristics of their disease), using the test to obtain a confidence of 95% and a power of 80%, it is estimated that the sample size it must be at least 10 subjects in each group (the objective of the study will be a minimum of 24 subjects to improve the statistical weight).

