#### 2) LIMITATIONS

The present study shows a series of limitations, most of them intrinsic to the difficulty of the object of the same and to the characteristics of the rehabilitation treatment. The aim of the study is to find indications of the efficacy of rTMS in the subacute phase for the improvement of the functionality of the upper extremity in stroke, which allows us to consider studies of a larger sample size and a more homogeneous sample.

- Strokes show great variability in etiology, location and response to rehabilitation treatment. We will try to perform a subanalysis of all these factors, although the sample size will not allow us to reach definitive conclusions.
- The radiological variables will be analyzed in a qualitative way, given the diverse origins with different characteristics of the patient's image tests
- The rehabilitative treatment, although it is protocolized, presents a variability marked by the necessary individualization (since we maintain the usual treatment of our center). This limitation is tried to compensate with the condition of blind for the condition of stimulation of the patient on the part of the therapist.
- The rhythm of patient recruitment can be variable given the characteristics of the patients who enter our center according to the stroke plan (patients with an important affectation, many of them severe and very severe in relation to the upper limb, and who in principle, it is unlikely that they can benefit from rTMS).

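### FM and ARA changes are compared without baseline adjustment, by a test that a normality check selects; one pre-set baseline-adjusted analysis per scale would be more precise under most, not all, assumptions

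*Combined protocol and SAP*

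**What the plan says.** The only comparison of the arms is in Material and Methods, 1) Design, under Statistical analysis: "Changes in the clinical scales (FM and ARA Test) between the two groups will be compared by means of nonparametric tests" (Mann-Whitney) or, "if the normality (Kolmogorov-Smirnov) is not rejected, the TTest test". No baseline covariate, ANCOVA or regression is named for it. The paragraph adds that "the response variables (in these three tests) will be related to various demographic, neurophysiological variables" and disease characteristics, but it gives no method and no adjusted contrast between arms. The subanalysis of stroke factors under 2) Limitations gives none either.

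On size, "it is estimated that the sample size it must be at least 10 subjects in each group", with a target of at least 24 in total. On timing, "Evaluations will be made before the intervention, at the end of the intervention and one month later", so there are two post-treatment visits. The statistics paragraph does not say which one the changes refer to. It also does not say how the Kolmogorov-Smirnov (KS) test is run: per arm or pooled, with or without the correction for estimated parameters. The Limitations section gives the purpose as finding indications of efficacy, "which allows us to consider studies of a larger sample size and a more homogeneous sample".

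**The concern.** A change score forces the slope of follow-up on baseline to be exactly 1. If the true slope is lower, change is negatively related to baseline. Noise is then left in the comparison, and a chance baseline difference between arms pushes the result in one direction. ANCOVA estimates the slope, and the baseline scores it needs are already collected.

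The rule for choosing the test is written in advance, but its outcome is not. The data decide whether a difference in means or a comparison of ranks is reported, and FM and ARA could end up with different ones. For planning a larger study, the useful product is a mean difference with its CI. A Mann-Whitney p-value alone does not supply that.

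For FM, baseline also bears on treatment content, since "there would be differences between a moderate patient (FM upper extremity motor between 22 and 45) and mild". That matters only where an imbalance crosses the cut at 45.

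**Working it through.** **Inputs.** From the plan: 95% confidence (two-sided 5% assumed), 80% power, 10 per group, target 24 (12 per arm if allocation is 1:1, which is not stated). Not in the plan, so varied: r, and k = follow-up SD / baseline SD. Effects d are in units of the SD of change.

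**The plan's own figure.** Ten per group cannot be reproduced, because no effect size or SD is given. Solved backwards for a two-sided t-test (noncentral t), it implies d = 1.325. At 12 per arm, power is 87.3% at d = 1.325 and 64.9% at d = 1.0.

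**Variance.** With baseline SD = 1:
- change score: V_c = 1 + k² − 2rk
- ANCOVA: V_a = k²(1 − r²), multiplied by 1 + 1/(N − 4) = 1 + 1/20 = 1.05 for the estimated slope at N = 24.

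Example, k = 1, r = 0.5: V_c = 1; V_a = 0.75; ratio 0.75 × 1.05 = 0.79.

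**Power.** Simulated with bivariate normal data, 12 per arm, 40,000 replicates per cell; each power cell is change t-test / ANCOVA, in %.

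| k | r | V_c | V_a | ratio × 1.05 | d = 1.0 | d = 1.325 |
|---|---|---|---|---|---|---|
| 1.0 | 0.5 | 1.00 | 0.750 | 0.79 | 65.1 / 75.1 | 87.4 / 93.8 |
| 1.0 | 0.7 | 0.60 | 0.510 | 0.89 | 64.8 / 69.7 | 87.3 / 90.7 |
| 1.0 | 0.8 | 0.40 | 0.360 | 0.945 | 64.9 / 67.2 | 87.4 / 89.1 |
| 1.0 | 0.9 | 0.20 | 0.190 | 0.997 | 64.9 / 65.0 | 87.4 / 87.3 |
| 0.8 | 0.5 | 0.84 | 0.480 | 0.60 | 65.0 / 85.5 | 87.4 / 97.8 |
| 0.8 | 0.7 | 0.52 | 0.326 | 0.66 | 65.1 / 82.1 | 87.0 / 96.5 |
| 0.8 | 0.8 | 0.36 | 0.230 | 0.67 | 64.7 / 81.6 | 87.3 / 96.5 |
| 0.8 | 0.9 | 0.20 | 0.122 | 0.64 | 64.7 / 83.4 | 87.7 / 97.1 |
| 1.2 | 0.5 | 1.24 | 1.080 | 0.915 | 65.0 / 68.8 | 87.5 / 90.1 |
| 1.2 | 0.7 | 0.76 | 0.734 | 1.015 | 64.9 / 64.3 | 87.3 / 86.9 |
| 1.2 | 0.8 | 0.52 | 0.518 | 1.047 | 64.7 / 62.7 | 87.2 / 85.5 |
| 1.2 | 0.9 | 0.28 | 0.274 | 1.026 | 65.4 / 64.1 | 87.4 / 86.4 |

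With equal SDs the 95% CI is 11, 5, 3 and 0% narrower at r = 0.5, 0.7, 0.8 and 0.9, and ANCOVA stops gaining at r of about 0.905. At k = 0.8 the CI is 18 to 22% narrower. On a wider grid (k = 0.7, 0.8, 1, 1.2; seven values of r from 0.3 to 0.95), ANCOVA has the smaller variance in 24 of 28 cells.

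**Chance imbalance.** The SE of the baseline difference is √(2/12) = 0.408 SD, so P(|difference| ≥ 0.5 SD) = 2(1 − Φ(0.5/0.408)) = 0.221. Within those trials, with no true effect (100,000 replicates), the planned test's false-positive rate at r = 0.5, 0.7, 0.8, 0.9 is:
- k = 1.0: 10.1, 8.2, 7.3, 6.1%
- k = 0.8: 14.4, 12.7, 12.7, 13.0%
- k = 1.2: 7.7, 5.7, 5.4, 5.6%

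ANCOVA is at 4.7 to 5.3% throughout. Over all trials the planned test is at 4.6 to 5.4%.

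**Test selection.** With uncorrected critical values, KS rejected in at most 1.7% of trials even with exponential residuals, so the plan is then nearly always a t-test. With Lilliefors values it switched to Mann-Whitney in about 9 to 11% of normal trials and 29 to 60% of skewed ones. With KS applied per arm, the two versions led to a different verdict in 1.0% (normal changes), 3.2% (gamma, shape 4) and 11.0% (exponential) of trials at d = 1.0, and in 0.5, 2.1 and 6.2% at d = 1.325.

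**Skewed residuals** (equal SDs, d = 1.0, r = 0.5/0.7/0.8/0.9):
- exponential: Mann-Whitney on change 72/75/77/79%, ANCOVA 77/72/71/69%
- gamma, shape 4: Mann-Whitney 64/65/66/66%, ANCOVA 76/70/68/66%.

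**The case against.** The planned comparison is valid in a randomised trial, the study is openly exploratory, and the gain rests on two quantities the documents do not give. This stands. It limits the point to efficiency and pre-specification, and most assumptions means most cells of a chosen grid.

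The entry rule (FM of at least 22) cuts baseline FM from below and so shrinks its variance. With a cut assumed 0.5 SD below the unselected mean and equal SDs before selection, the gain at r = 0.5/0.7/0.8/0.9 falls to about +4/+1 to +2/0/−1 points. This also stands for FM, but it acts like an SD ratio above 1, which the k = 1.2 rows cover. A ceiling on the scale would push the other way.

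The conditional false-positive rates have an offset. If the overall rate is 5%, 10.1% in the imbalanced trials implies (5 − 0.221 × 10.1)/0.779 = 3.6% in the rest. That is correct. Protection against imbalance and precision are largely one benefit seen from two sides.

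Under strong skew, a Lilliefors-selected test has 71/74/75/77% power against 77/73/71/69% for ANCOVA, so the present plan would be stronger from r = 0.7 up. With uncorrected KS it has 68/68/68/70%, close to or below ANCOVA except at r = 0.9. This is the best reason to keep Mann-Whitney in the report.

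The rarity of uncorrected KS rejection, and the fact that the t-test branch does yield a mean difference and CI, weaken the reporting argument. They do not touch the adjustment argument. Finally, the sentence on relating responses to other variables is garbled: it refers to three tests after naming two scales. Its intended method cannot be recovered, but as written it is not an adjusted comparison of arms.

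**Conclusion.** The concern holds as a low-cost improvement to consider, with moderate confidence. As written, baseline enters only by subtraction and the reported estimand depends on a normality test whose version is not stated. Type I error is sound.

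With 12 per arm and normal data, ANCOVA ranges from a gain of about 20 power points (follow-up SD 0.8 of baseline) to a loss of up to 2 (follow-up SD 1.2 of baseline, r = 0.7 to 0.9). With equal SDs the gain is 10 points at r = 0.5 and disappears at r of about 0.9. With strongly skewed residuals, Mann-Whitney on change is stronger from r = 0.7 up. All of this assumes 1:1 allocation and a two-sided 5% test.

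**What to change.** Replace the KS-dependent choice with one pre-specified analysis for each of FM and ARA, at one named post-treatment visit of the investigators' choosing: ANCOVA of the follow-up score on arm and the baseline score of the same scale, reported as an adjusted difference with 95% CI. Report Mann-Whitney on change every time as a fixed sensitivity analysis, whatever the distribution looks like. The KS test is then not needed, and the question of its version goes away. Which scale leads is a separate matter that this change does not settle.

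Optionally, if the randomisation plan due in month 1 is stratified by FM band (22 to 45, above 45), include the band in the model.

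The cost is a rewritten sentence and one degree of freedom, with no extra data, visits or patients. The price in power is at most about 2 points in the normal-data cases shown. It is larger under strong skew with high r: 79% for Mann-Whitney against 69% for ANCOVA at r = 0.9 with exponential residuals. The fixed sensitivity analysis is there to reveal that case.

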#### 2) LIMITATIONS

The present study shows a series of limitations, most of them intrinsic to the difficulty of the object of the same and to the characteristics of the rehabilitation treatment. The aim of the study is to find indications of the efficacy of rTMS in the subacute phase for the improvement of the functionality of the upper extremity in stroke, which allows us to consider studies of a larger sample size and a more homogeneous sample.

- Strokes show great variability in etiology, location and response to rehabilitation treatment. We will try to perform a subanalysis of all these factors, although the sample size will not allow us to reach definitive conclusions.
- The radiological variables will be analyzed in a qualitative way, given the diverse origins with different characteristics of the patient's image tests
- The rehabilitative treatment, although it is protocolized, presents a variability marked by the necessary individualization (since we maintain the usual treatment of our center). This limitation is tried to compensate with the condition of blind for the condition of stimulation of the patient on the part of the therapist.
- The rhythm of patient recruitment can be variable given the characteristics of the patients who enter our center according to the stroke plan (patients with an important affectation, many of them severe and very severe in relation to the upper limb, and who in principle, it is unlikely that they can benefit from rTMS).

#### Pla de Treball:

Recruitment of patients for the study: 15 month period

Duration of the study: 18 months

### - 1st month:

Start-up of the study, assessing in an initial patient the mechanics of evaluation and intervention measures in a coordinated manner. Randomization plan for patients. Before start the study will register the same in the trials.gov page

# -2nd to 15th month:

Carrying out of the study, with the realization of the first clinical and neurophysiological evaluation of each patient the week before performing the rTMS and the week after the end of the stimulation. A new clinical evaluation will be carried out at 4 weeks (± 1 week)

- 14th to 18th month:

Analysis of the data and starting of their dissemination.

ERES	IN STITUT GUTTMANN HOSPITAL DE NEURODEHABILITACIÓ Institut Universitari adsorit a la UMB
